## 5. What happens to participants on study intervention when the study ends?

Participants will continue to receive their usual care at HFH (and/or elsewhere)

## 6. Describe the process for referring participants to care outside the study, if needed.

Prior to initiation of the study, all medical staff based at the Department of Obstetrics of HFH will be trained/oriented in WHO's mhGAP guidelines to address take part in the process of making referrals from non-specialist providers or interviewers. Such referrals will be made to the Institute of Psychiatry (IoP) in Rawalpindi, the district tertiary care hospital, or the teaching hospital. These centers are staffed by experienced and qualified psychiatrists and other mental health professionals who routinely provide a range of services. The IoP is also the WHO Collaborating Centre for Mental Health Research and Training in Pakistan. They also have an established social services for persons affected by domestic violence.

Any woman showing signs of severe depression or suicidality at any point during the study will be noted by the HMHB trainer or assessment team members or hospital staff (antenatal staff) and reported to [name] a psychologist [name], a psychiatrist for further evaluation. Based on their clinical judgement referred psychiatric and/or psychological care as is necessary. As mentioned above HMHB therapists, the assessment team and hospital staff in the Obstetrics Department will be trained in the WHO's mhGAP guidelines. For a woman without life-threatening conditions but with high symptom levels of anxiety or depression, her obstetrician will be alerted to undertake further assessment and to make appropriate referrals. Women who report IPV will be referred to the IoP for social services. Because domestic

violence against women is highly prevalent in Pakistan, we are in the process of reviewing additional potential interventions strategies to be incorporated in the HMHB intervention program. Women needing general medical care will be referred within the hospital facilities.

## **VI. Data Security and Confidentiality Protections:**

### **1. Personally Identifiable Information (PII):**

Please identify the Personally Identifiable Information (PII) that you may be collecting and using at any of the following stages of your study: ***Recruitment, Consent, and Study Implementation.***

Name, signature, initials, or other identifiable code	
Geographic identifier: address, GPS location, etc.	
Dates: birth, death, clinical service, discharge, etc.	
Contact information: phone numbers, email address, etc.	
ID: Social Security Number, driver's license number, etc.	
Health record identifiers: medical record, insurance plan number, etc.	
Account numbers	
Device identifiers: e.g., implants	
Internet identifiers: IP address, social media accounts	
Biometric identifiers, including finger and voice prints	
Audio recordings	
Video or full face photographic images	
Genomic/genetic data	
Any other unique identifying number, characteristic, or code (note: this does not mean the unique code assigned by the investigator to code the data)	
Other: Click here to enter text.	

### **2. Recruitment:**

Will you collect identifiers for the purpose of contacting potential participants? Yes  No

If yes, will you retain the identifiers after the recruitment contact has been made? Yes  No

### **3. Data Collection:**

Collection of data for a research study can take on many forms. It can be as simple as gathering the data with pen and paper or developing an on-line adaptive survey that changes based on the participant's answers. Regardless of the method, PII for the purposes of identifying the participants will most likely be collected. Once collected, the raw data should go through a de-identification process to further protect PII.

In what form will you collect and store PII? When you respond, think of PII collected for recruitment, consent, and other study purposes.

1. **Hard Copy/Paper:** Yes  No 

If yes, please answer the following:

## A. How will the data be kept secure during transfer from study collection site to storage site?

Any data in the form of paper or hard copies (i.e. consent forms, log of women screened) will be kept in a locked bag to be carried by one of our research staff members to the central HDRF office where the data manager will also have an identical set of keys to open the bag. These data should be delivered by means of same-day dispatch. Paper documents with personal information including consent forms will be kept in a locked filing cabinet. The key will be kept with the data manager. All personal information will be confidential and will not be shared or discussed with individuals outside the team without participant consent (e.g. in the case of a clinical referral). Encrypted study participant research data, which is for purposes of statistical analysis and scientific reporting, will be collected on tablets. These tablets will be connected to a central server and transmitted to and stored at the HDRF data coordinating center. This will not include the participant's contact or identifying information. Rather, individual participants and their research data will be identified by a unique study identification number. The study data entry (e.g. the tablets) and study management systems used by the clinical site, by the HDRF data Coordinating Center and research staff will be secured and password protected. This password will be updated on a monthly basis. After each wave of data collection data will also be sent to JHSPH and stored on JHBox. At the end of the study, all study databases will be de-identified and archived at the NIMH data repository.

Biological data will be generated by [name] and will be stored on a secure server in the Department of Psychiatry.

B. Will the data be secured in a locked cabinet or room? Yes  No C. If study IDs/Codes are used, will they be stored separately from the study data? Yes  No 

## D. Will the hard copy/paper be destroyed after data abstraction and cleaning are complete?

Yes  No

If No, when do you plan to destroy the hard copies?

2. **Electronic:** Yes  No 

If yes, please answer the following:

- Will the data be collected/stored on a portable device (laptop, mobile phone, tablet, PDA) protected by encryption? Yes  No

- Will study participants use personally owned devices or study-provided devices?  
Personally owned  Study provided

- Is the application/website used for data collection being developed in-house (Hopkins) or by a 3rd party vendor?  
In-house  3rd party

If 3rd party, provide the name of vendor and URL:

Identify Mobile Ecosystem (check all that apply) Apple  Google  Website

- Will the data be stored on a secure server (@JHSPH/on-site)? Yes  No

- Will the data be stored in the Cloud/Web? Yes  No
- Will it be encrypted? Yes  No
- Will you be backing up your data? Yes  No

3. **Audio Recording:** Yes  No

If yes, please answer the following:

1. Will you store the audio recording securely in a locked cabinet/room until transcription is complete?  
Yes  No
2. Will you use a transcription service?  
Yes  No   
If yes, if the PII comes from JHH/JHHS, you must use an approved vendor; otherwise, be aware of the data security protections that the transcription service provides.
3. Will the audio recording be destroyed after transcription? Yes  No

If no, why not?

- **Photograph/Video:** Yes  No

If yes, please answer the following:

- Will the photographs/videos be stored securely in a locked cabinet or room? Yes  No
- Will the photograph/video be destroyed? Yes  No

If yes, when?

4. **PII De-Identification of Data Used for this Study:**

- When will you destroy the PII and/or the code linking the PII with the study ID?

While the data will be deidentified for the purposes of analysis, the data code linking the PII and study ID will be destroyed after analysis of these data is complete.

- What is the method you will use to de-identify the data?

At the end of the data collection period and after all data has been cleaned, analytic datasets will be stripped of names of participants. Datasets will retain the unique study number for each participant.

- Is your research data governed by HIPAA (U.S. clinical data remaining within the covered entity)?
 

Yes  No

  - If yes, who is doing the de-identification?
  - If yes, what level of de-identification will you achieve (Limited data set? De-identified?)

## 5. **Data Storage and Analysis:**

One of the keys to protecting PII is the proper use of tools to share and conduct your analysis. JH and JHSPH offers several options for you to consider. Please select the system that you plan to use to protect your study data by clicking the box. Consult JHSPH IT for assistance if needed.

- JH Virtual Desktop:** The Hopkins Institute for Clinical and Translational Research (ICTR) provides a virtual Windows desktop (SAFE Desktop). It includes productivity software such as Microsoft Word and Excel, as well as statistical software, including SAS, Stata, R, R Studio, and Python. 100 GB of storage space is provided.
- JHSPH SharePoint and File Shares:** These systems provide a managed and secure platform for your research project. They also provide a built-in encrypted backup solution.
- JHSPH RedCAP:** These are departmentally managed applications. RedCAP is an application designed for collaborative research projects.
- JHSPH HPCC:** High Performance Computing Cluster (HPCC: <https://jhpce.jhu.edu/>) can provide the high capacity computing required for very large data sets.
- JHBox:** Johns Hopkins Box (JHBox) is a secure cloud-based file sharing service which enables people to collaborate and share information and may be accessed through any device: desktop, laptop, phone, or tablet with appropriate permissions. JHSPH IT recommends that investigators not use JHBox as a primary storage location, but use it instead for initial data collection, sharing results, and other collaborative information with the research team.
- Independent Departmental Servers and Systems:** These servers are typically managed by departmental or research team IT staff. Because these servers are not centrally managed by JHSPH IT, all documentation regarding data security protections will need to be provided by the owner/administrator of the server. This responsibility may fall to the data owners (PI).
- Other:** Please provide details regarding any other systems being utilized. Examples may include servers and applications located at another university participating in your study or a 3rd party web-based application.

Any data in the form of paper or hard copies (i.e. consent forms, log of women screened) will be kept in a locked bag to be carried by one of our research staff members to the central HDRF office where the data manager will also have an identical set of keys to open the bag. These data should be delivered by means of same-day dispatch. Paper documents with personal information including consent forms will be kept in a locked filing cabinet. The key will be kept with the data manager. All personal information will be confidential and will not be shared or discussed with individuals outside the team without participant consent (e.g. in the case of a clinical referral). Encrypted study participant research data, which is for purposes of statistical analysis and scientific reporting, will be collected on tablets. These tablets will be connected to a central server and transmitted to and stored at the HDRF data coordinating center. This will not include the participant's contact or identifying information. Rather, individual participants and their research data will be identified by a unique study identification number. The study data entry (e.g. the tablets) and study management systems used by the clinical site, by the HDRF data Coordinating Center and research staff will be secured and password protected. This password will be updated on a monthly basis. After each wave of data collection data will also be sent to JHSPH and stored on JHBox. At the end of the study, all study databases will be de-identified and archived at the NIMH data repository.

During data collection at the hospital, all the data collected on tablets will be submitted on the server via internet at the end of each working day. No data will remain on tablets at the end of the day. The data will be sent to the HDRF server on daily basis once the interview is over. The Assessment Team members will confirm with the HDRF data manager that he has received the submitted forms. Data will not be deleted from tablets without the consent of the data manager. Open Data Kit (ODK) forms are autosaved so that there is no chance of losing the data. The assessment team and the data manager will remain in communication to ensure proper management of data. The data manager will check the online submission of data before closing of each day and will verify the submission of data on the web server on daily basis. The data manager must make daily backups of the trial data and will keep those backups both at Holy Family Hospital and at the HDRF office. Only the data manager will have access to the ODK web server. The data manager will share a weekly report with the site PI and project manager including an enrollment table that will have the screening details of the trial participants and their numbers per trial arm. The data manager and trial manager will make a weekly report (including SAE, refusal cases, missing data etc.) to be shared at the end of each week with PI. The informed consent forms will be stored in a separate HMHB locked cupboard and their log must be maintained by the assessment team lead, it will be checked on daily basis for the correct date, signature or thumb prints (whichever is applicable). At the end of each day, a data cleaning process will take place before finalization and sending the forms.

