In our study, the unit of randomization is an individual woman, with an equal number of women randomized to the intervention and control groups. We assume an outcome prevalence of CMDs (postnatal depression episode and anxiety) at 30%, which is conservative given that most estimates of prenatal depression in Pakistan are higher than this. (16, 17, 91, 129) While we observed a 50% reduction in postnatal depressive symptoms when evaluating our prior CBT intervention (which was initiated late in pregnancy), we desire 85% power to detect reductions in CMDs as low as 30% (86, 130, 131), requiring 840 pregnant women (420 in each arm). Anticipating 30% attrition post enrollment, we will enroll 600 women per group in this study, for a total of 1200 women. This sample size of 420 outcomes per group provides ample power to detect important reductions in SGA, which we currently estimate to occur in approximately 47% of births. For example, we will have 90% and 80% power to detect reductions of 23.7% and 20.2%, respectively.

Sample size considerations for the qualitative process evaluation/COVID-questions will be based on a target number of up to 80 women sampled across different characteristics, or until saturation is achieved. We will sample up to 45 women from the intervention group and 25 women from the EUC group and another 10 who dropped out of the intervention. As described (See under Study Design above), these women will be purposively sampled to achieve a wide range of variation (or maximum variation) on various dimensions of interest. To triangulate and learn from multiple perspectives, we will also hold 2 focus group discussions (FGDs) with the HMHB therapists and assessors/screeners involved in delivery, assessments, or coordination of the intervention to ask them about their perspective on the same issues. Topics of interest for sub-group analyses include the effects of transitioning from in-person to by-phone format during the COVID pandemic, distress related to COVID-19, and the effects of prior miscarriage on current pregnancy and intervention experience.

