Recruitment / Consent / Randomization: Pregnant women coming for their initial prenatal visit will be screened for eligibility; this includes being “at risk” for anxiety on the anxiety subscale of the Hospital Anxiety and Depression Scale (HADS) or having moderate or high levels of anxiety (i.e. a cutoff of  $\geq$  score of 8). Informed consent will be obtained from eligible women and those agreeing to participate will be individually randomized to either the HMHB intervention or enhanced usual care (the control). A randomization sequence with varying block size (i.e. randomly permuted sizes of 4, 6, 8, and 10) will be generated by an independent researcher who is located off-site (Institute of Psychiatry, Rawalpindi, Pakistan) and is not involved in running of the study. The individual allocations will be provided to the study staff in opaque sequentially-numbered envelopes and utilized sequentially at the time of enrollment of each participant. Each woman randomized into the HMHB group will be assigned to a HMHB non-specialist provider to introduce them to the program.

Intervention Group: Women allocated to this group will receive the HMHB intervention. The content of HMHB will be based on 1) formative research (completed last year), 2) prior cognitive behavior therapy-based approaches to

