## Moderator Analysis

To examine potential effect modifiers of the intervention treatment effects on birth outcomes, we will expand the regression models to include a term for the interaction between intervention group status and the potential moderators (exposure to social support, stress levels, marital relationship and empowerment measured at baseline as well as retrospective report of IPV measured at 6 weeks postpartum). This will allow us to examine whether the effects of HMHB differ for mothers (or their children) with varying levels of the potential moderators; analyses will be informed by recommendations in Aiken and West (1991)(140) and Preacher et al. (2006) (141). This aim will be exploratory given limited power for detecting interaction effects.

5. **Answer the following if they are relevant to your study design:**

- If the study has different arms, explain the process for assigning participants (intervention/control, case/control), including the sequence and timing of the assignment.

Study statistician will produce a random sequence of assignments to the study arms. This sequence will be generated using a pseudo random-number generator, and will be constructed using randomly permuted blocks of size 4, 8, 12, and 16. The assignment list will be printed in order, with each step of the sequence separately stored in opaque envelopes and numbered sequentially. When an individual who has been determined as eligible via the screening procedure subsequently provides consent for study participation, the X will pull the next available envelope, opening it, and recording the assignment to intervention or control.

In addition to the participants randomized through the main study, there will be three arms for the biological study. We will choose the first 100 participants each in the intervention and control arms, and will also recruit a group of 100 healthy controls (HADS <8) who will participate only in the biological study.

- If human biospecimens (blood, urine, saliva, etc.) will be collected, provide details about who will collect the specimen, the volume (ml) and frequency of collection, how the specimen will be used, stored, identified, and disposed of when the study is over. If specimens will be collected for use in future research (beyond this study), complete the "Biospecimen Repository" section below.
-

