The proposed study is a single-blind, individual randomized clinical trial. The assessment team, trial statistician, and PIs will be masked to allocation status of study participants. To maintain masking during the trial, intervention and assessment teams will not have any interaction during the trial, as they will be placed at separate locations within the Obstetrics Department of HFH. Furthermore, participants will be instructed not to disclose which type of treatment they are receiving to the assessment team. Fidelity of masking will be measured by having assessors guess the trial arm of each participant at the end of follow-up assessment. We hypothesize that assessors will only be able to correctly guess the condition of participants at a chance rate of nearly 50% at follow-up assessments, indicating that masking is maintained.

2. Will participants receive standard care or have current therapy stopped?

Each woman randomized into the HMHB intervention arm will receive the HMHB intervention program plus usual care. Women allocated to the control condition will get usual care (slightly enhanced) alone. The WHO recommends eight antenatal visits for positive pregnancy experience (43) which we will be the target number of visits for study participants in the control group (depending on their gestational week). These visits will involve evaluating health status, discussing any concerns, and performing routine exams consistent with stage of pregnancy. Usual care will also be enhanced by medical staff at the hospital receiving additional training in mental health treatment to counsel participants. Transportation will also be provided or facilitated for participants to assist with attending appointments and the study will pay for any ultrasounds needed.

3. Will you use a placebo or non-treatment group, and is that justifiable?

The control arm will receive a slightly enhanced version of usual care, which we consider is justifiable.

4. Explain when you may remove a participant from the study.

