4. If the PI will not personally be on-site throughout the data collection process, provide details about PI site visits, the supervision over consent and data collection, and the communication plan between the PI and study team.

The PI will have weekly calls with the team, and local supervision of consent and data collection will be monitored by Drs. [name] and [name] (as described above in #1). The PI will also make at minimum yearly site visits. The leadership team will meet in Baltimore and Liverpool once a year for face-to-face team meeting (including not only Drs. [name], [name], [name], [name] and [name] but also including [name]). Drs. [name] and [name] will participate in the Baltimore based face-to-face meetings.

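### A weekly enrolment table by arm goes to the site PI although PIs are declared masked; under permuted blocks it also gives partial information about the next allocation

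*Combined protocol and SAP*

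**What the plan says.** Three parts of the plan bear on this.

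- **Weekly report (Section VI.5, Data Storage and Analysis).** "The data manager will share a weekly report with the site PI and project manager including an enrollment table", and that table is described as "an enrollment table that will have the screening details of the trial participants and their numbers per trial arm". Nothing says that the arms are coded, that the counts are cumulative or for the week only, or that recipients are kept apart from enrolment.
- **Masking (Section V, answer on whether study staff are blind).** "The assessment team, trial statistician, and PIs will be masked to allocation status of study participants". The site PI is not excepted. The project manager is not on the list.
- **Randomisation.** The plan foresees individual 1:1 allocation, "with an equal number of women randomized to the intervention and control groups" (Section III.B), at one hospital and with no stratification described. Blocks vary in size, but the two descriptions differ. The recruitment and randomisation paragraph of Section V gives "randomly permuted sizes of 4, 6, 8, and 10". The later answer on assigning participants to arms says the sequence "will be constructed using randomly permuted blocks of size 4, 8, 12, and 16". Both use opaque, sequentially numbered envelopes.

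On roles, Section V.B gives screening and consent to the Assessment Team. Section X.A.4 says "local supervision of consent and data collection will be monitored by" local senior investigators.

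**The concern.** Varying block sizes and opaque envelopes serve one purpose: nobody who can influence enrolment should be able to anticipate the next assignment. In a permuted-block list, any difference between the running arm totals must be repaid before the current block closes. Someone who sees those totals therefore knows that the lagging arm is more likely to come next.

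Two things are at stake. The first is consistency: a person declared masked receives arm-level information as routine. The second is allocation concealment. If the information reached recruiters, the timing of an enrolment could be influenced. There is some slack for that, because an eligible woman may take up to 14 days to decide (Section V.B).

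**Working it through.** The documents give no figure for predictability, so there is none to reproduce.

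**Inputs from the plan:** 1:1 allocation; 1,200 women; one unstratified list; block sizes 4/6/8/10 or 4/8/12/16.

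**Assumptions:** block sizes are equally likely; the reported counts are cumulative; the guesser picks the arm with fewer women and tosses a coin when the arms are level; weekly enrolment is 5 to 30. The documents state none of these.

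**Step 1: the first allocation after a report.** Suppose that in a block of size b, i places are used and t of them went to intervention. For a randomly chosen next participant:

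- P(b, i, t) = (1/Σb) × C(i, t) × C(b−i, b/2−t) / C(b, b/2), with Σb = 28 or 40
- P(next is intervention) = (b/2 − t)/(b − i)
- difference in arm totals D = 2t − i

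Summing over b, i and t gives:

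| Absolute D | 4/6/8/10: share of time | lagging arm next | 4/8/12/16: share of time | lagging arm next |
|---|---|---|---|---|
| 0 | 34.2% | 50% | 29.6% | 50% |
| 1 | 46.7% | 73.3% | 43.2% | 68.6% |
| 2 | 15.3% | 81.3% | 18.5% | 73.3% |
| 3 | 3.3% | 87.4% | 6.4% | 77.0% |
| 4 | 0.44% | 93.6% | 1.8% | 81.2% |
| 5 or more | 0.03% | 100% | 0.47% | 85% to 100% |

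Weighting the guess by the share of time:

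- Blocks 4/6/8/10: 0.342×0.5 + 0.467×0.733 + 0.153×0.813 + 0.033×0.874 + 0.0044×0.936 + 0.0003×1 = **67.1%**
- Blocks 4/8/12/16, by the same sum: **64.8%**
- Without arm counts: **50%**

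A certain prediction arises for less than 0.03% of allocations under either list.

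**Step 2: the whole following week.** The lead is repaid once and then carries no more information. I simulated 1,500 lists of 1,200 with Poisson weekly enrolment and applied the same guess to every allocation in the next week:

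| Enrolments per week | 4/6/8/10 | 4/8/12/16 |
|---|---|---|
| 5 | 58.3% | 58.5% |
| 8 | 55.5% | 56.3% |
| 10 | 54.5% | 55.3% |
| 20 | 52.2% | 52.7% |
| 30 | 51.5% | 51.8% |

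**Step 3: cross-check.** The expected number of extra correct guesses per report cannot exceed half the mean absolute D. For 4/6/8/10 that mean is 0.467×1 + 0.153×2 + 0.033×3 + 0.0044×4 + 0.0003×5 = 0.89. The gain is then at most 0.89/2 = 0.45 guesses per report. At 8 a week the ceiling is 0.5 + 0.45/8 = 55.6%, which agrees with the simulated 55.5%. For 4/8/12/16 the mean is 1.09, so the ceiling is 0.5 + 0.55/8 = 56.8%, against 56.3% simulated. The shortfall is expected, because some of the longer blocks are still open a week later.

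**The case against.** The case on the other side is substantial, and most of it limits the point rather than removing it.

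- **A total is not an individual's allocation.** The masking statement concerns participants' allocation status, and the table can be read as screening details plus arm totals. This stands: the conflict is direct only if women are listed by arm. The project manager is not declared masked at all.
- **The table does not name the next arm.** A reader might infer that it does. It shifts a probability, and only if the counts are cumulative, which Section VI.5 does not say. A reader might also take up the figures for reports that show an imbalance (66% or 70% of weeks, with the next guess right in 76% or 71% of them). Those are correct but cover only the most informative moment. The figures over all reports and over the week describe the leak better.
- **Recipients do not recruit.** The Assessment Team screens and consents, and the table is not sent to them. This stands, but the separation is thin. Local investigators oversee consent (Section X.A.4). The data manager sits on the steering committee (Section VII), which meets weekly during enrolment (Section X.A.1), and stays in contact with the Assessment Team (Section VI.5).
- **Whoever opens the envelopes can keep an exact tally anyway.** This is true, and removing the arm column does not change it. It does stop the information from spreading to others.
- **Someone needs arm counts.** This also stands. The biological substudy takes the first 100 women in each arm, and every intervention woman is assigned a provider (Section V). It would be wrong to say that arm counts have no use, or that only the DSMB should hold them.

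**Conclusion.** The plan declares PIs masked and also sends the site PI a weekly arm-level table, and nothing in it reconciles the two. If the counts are cumulative, the table raises the chance of guessing the first allocation after a report from 50% to about 65-67%. Averaged over the following week, the chance is about 58% at 5 enrolments, 55-56% at 8 and 52-53% at 20. This rests on equally likely block sizes and assumed accrual rates; the conclusion is the same under either block-size list.

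A reader might infer that enrolment will be biased or that the primary outcome assessment is unmasked. The documents do not support either. No provision sends the table to recruiters, and the six-week assessment is made by the Assessment Team, which is declared masked and is not a recipient. Any effect on the trial result is probably small. The point is minor, and worth correcting because the correction is easy.

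**What to change.** 1. In Section VI.5, remove the arm breakdown from the weekly report to the site PI and project manager. Report only totals screened, eligible, consented and randomised. The same section already describes a second weekly report to the PI (serious adverse events, refusals, missing data) with no arm split mentioned, so reporting without arms is workable.
2. Send arm counts to the DSMB and to one designated unmasked person with no role in recruitment or outcome assessment. That person tracks the substudy quota of 100 women per arm and the assignment of providers.
3. Name that role in the masking answer in Section V, so that the two sections agree.

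The cost is a changed report template and one unmasked role designated from existing staff. The site PI loses a routine check on balance, which the blocks already keep close. Keeping the table and amending the masking statement to admit it would remove the contradiction but not the leak.
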